9.1. Study Design

This is a multi-country, multi-source, cross-sectional, descriptive study using longitudinal data collected from European EHR databases.

Several countries will be selected from the databases under consideration (France, Germany, Spain, Sweden, and the UK). The justification of the selected countries will be based on the feasibility assessment results (Section 9.5.2) and the market uptake and volume of dulaglutide in each country.

Study period

The study will be conducted for at least three years post launch of dulaglutide (January 2015). The analyses and reporting will commence approximately one year after the launch of dulaglutide, as soon as the data on 1000 initiations of dulaglutide are available in the databases with at least 100 cases available in the smallest contributing country.

Three waves of data extraction/collection and analysis will be performed within at least three years, based on launch projections:

- 1st wave: Q3 2016 (covering patients having initiated the drug from Q1 to Q4 2015)
- 2nd wave: Q2 2017 (covering patients having initiated the drug from Q1 to Q4 2016)
- 3rd wave: Q2 2018 (covering patients having initiated the drug from Q1 to Q4 2017)

9.2. Setting and Population

9.2.1. Setting

This study will be conducted using electronic longitudinal databases including data collected in outpatient settings of the target countries.

9.2.2. Inclusion Criteria

The eligible patients are those who meet the following criteria:

- Patients for whom a treatment with dulaglutide is initiated during the observation period.
- Patients having at least 6 months of available continuous history prior to the date of the first dulaglutide prescription.

No exclusion criteria will be applied to the study.

9.2.3. Population of Interest

The population of interest includes all patients receiving an initiation of dulaglutide during the observation period for each wave of the study. The use of dulaglutide will be analysed overall and within the following subgroups of patients.

- Populations of interest:

- Patients with severe renal failure
 - Patients with hepatic disease
 - Patients with heart failure
 - Patients with severe gastrointestinal disease
 - Children and adolescents <18 years of age
 - Elderly patients ≥ 75 years
 - Pregnant and breastfeeding women
- Medication use:
 - Medication errors
 - Off-label use

9.3. Variables

Regardless of the coding system used in the database, different populations and subgroups of interest are defined as follows:

Treatment initiation with dulaglutide:

- any record of prescription of dulaglutide during the observation period without prior record of prescription of the same product in the available patient's history
- if no prior history is available to check the above criteria, the prescription is not considered as an initiation

Patients presenting with T2DM:

- with any recorded diagnosis code for T2DM
- or with any recorded treatment code for an ADM other than insulin
- or, with any recorded treatment code for insulin initiated at age >30 (defined as no record of insulin therapy during 6 months prior to first record of insulin treatment)
- or with any record of unspecified diabetes mellitus diagnosis at age >30 and without history of insulin therapy (defined as no record of insulin therapy during 6 months prior to first record of diabetes diagnosis),
- a sensitivity analysis will be conducted to determine the age threshold mentioned above (see section 9.7.3 Sensitivity analysis).

Patients with severe renal failure:

- with a recorded diagnosis of severe renal failure
- or with a recorded glomerular filtration rate (eGFR) value <30 ml/min/1.73 m²

Patients with hepatic disease:

- with a recorded diagnosis of any hepatic disorder

Patients with heart failure:

- with a recorded diagnosis of heart failure

Patients with severe gastrointestinal disease:

- with a recorded diagnosis of any of the following conditions:
 - cancer of the gastrointestinal tract,
 - diseases of the oesophagus,
 - active ulcer at the time of drug initiation (gastric, duodenal, gastro-jejunal, peptic ulcer of unspecified site),
 - active haemorrhagic gastritis, chronic atrophic gastritis, adult hypertrophic pyloric stenosis, obstruction of duodenum, and other motility disorders,
 - digestive fistula,
 - Crohn's disease, ulcerative colitis,
 - diverticular disease of the intestine,
 - severe vomiting, severe diarrhoea and severe constipation
 - motility disorders, including ileus, gastroparesis, et cetera,
 - infectious and inflammatory situations (appendicitis, cholecystitis, cholangitis).

Children and adolescents:

- Age < 18 at the time of treatment initiation
(subgroups of analysis: 0-4, 5-9, 10-14, and 15-17 years old).

Elderly:

- Age \geq 75 at the time of treatment initiation.

Pregnant and breastfeeding women:

- Any record of pregnancy or breast feeding at the time of treatment initiation.

Patients with medication errors:

- Prescribed and/or administered > 1 dose per week of dulaglutide (6).
- The number of doses/week will be calculated by measuring the time span between the current prescription and the next one (in weeks) and dividing the number of injections prescribed in the current prescription by this time span. This number of doses/week will be used in the cross sectional study as an attribute of the prescription to assess the occurrence of medication errors as described above.

Patients with off-label use:

- Prescribed dulaglutide with no diagnosis of T2DM as defined above, at the beginning of this list of subgroups of populations.
- Prescribed dulaglutide with a diagnosis of T2DM as defined above and without a record of other ADMs during the 6-month baseline period, i.e. dulaglutide was prescribed as first-line therapy.

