9.3.2. Collected variables

To assess the above subgroups and measurements of interest, several variables will be extracted from each database whenever available: demographics, medical history, treatment, clinical and clinical laboratory data on patients. These variables along with their corresponding International Classification of Disease, 10th version (ICD-10) codes are presented in this protocol (Table 9.3.2-1). For CPRD database, the corresponding Read codes will be specified in the statistical analysis plan (SAP).

Table 9.3.2-1. Variables, Subgroups and Measurements of Interest in Dulaglutide Initiators

Variable, subgroup or outcome/measurement	Definition and categories*
Patients demographics at initiation of dulaglutide use: Age Gender BMI categories, Countries	< 18, 18-44, 45-64, 65-74, ≥75 years Male or Female Weight (kg) / Height (cm) ² < 18.5, 18.5-25, 26-30, > 30 kg/m ² UK, Germany, Sweden (or Spain and France)
Co-morbidities , at initiation of treatment to identify the subgroups of interest: 
 • History of severe renal failure • Heart failure • Hepatic disease • Severe gastrointestinal disease • Children and adolescents • Elderly • Pregnant women • Breastfeeding women 	ICD-10 code N18.5, N18.5 ICD-10 codes I50, I11, I13 ICD-10 codes B18, K70-K77, C22 ICD-10 codes C15-C26 K22.0, K22.1, K22.2 -K22.6, K23-K28, K29.0, K29.4 K50, K51, K55, K57 Age < 18 (subgroups: 0-4, 5-9, 10-14, 15-17 years) Age ≥ 75 ICD-10 codes: A34, E23.0, F53, M83, O00-O99, O24.1, O24.3, O24.9, Z32-Z36, Z39 Z39.1
Lab tests values (if available): 
 • Haemoglobin A1c (HbA1c) • e-GFR • Serum Creatinine Urine albumin/creatinine ratio (UACR) 
 • LDL-C (LDL-cholesterol) • HDL-C (HDL-cholesterol) • AST/ALT • Bilirubin • Beta hCG 	Abnormal values: < 6.5%, ≥6.5% eGFR value < 30 ml/min/1.73 m ² < 120, ≥120 µmol/L or mg/dL (male) < 100, ≥100 µmol/L or mg/dL (female) UACR >30 mg/g: albuminuria present: < 1.6, ≥ 1.6 g/L < 0.35 g/L, ≥0.35 g/L ≤ 2 or > 2 times upper limit of the normal range < 2, >7mg/L Positive

Variables, Subgroups and Measurements of Interest

Variable, subgroup or outcome/measurement	Definition and categories*

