History of other medications , during 6-month baseline period	
 • ATC code or associated medcode for main pharmacological classes.
Off-Label Use	
 • Patients without T2DM • Patients with T2DM for whom dulaglutide was prescribed as first-line therapy

Variable, subgroup or outcome/measurement	Definition and categories*
T2DM	Any of the below conditions: 
 • ICD-10 code E11 • ATC codes A10P or A10X • ATC codes A10A initiated at age>30 • ICD-10 codes E14 first recorded at age>30 without ATC code A10A in the previous 6 months

Abbreviations: ALT= alanine amino transferase; AST= aspartate amino transferase; Beta hCG=Beta subunit of human chorionic gonadotrophin; BMI= body mass index; eGFR= estimated glomular filtration rate; HDL-C= high density lipoprotein cholesterol; ICD-10= International classification of disease, 10th version; LDL-C= low density lipoprotein cholesterol; T2DM= type 2 diabetes mellitus; UK= United Kingdom.

* continuous variables will be also presented by means, SD, et cetera.

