9.4.3. NPR and SPDR in Sweden

Swedish data combine data from the NPR, covering all specialist and hospital care in Sweden, and the SPDR, covering all drugs dispensed at pharmacies in Sweden. The national registers are

updated at least quarterly. These longitudinal data enable to find out comorbidities and historical clinical information on the subjects treated for their T2DM in a hospital, as well as drug prescription details (both primary and secondary care). Prescriptions are not formally linked to an ICD-10 code, but clinical input could provide rationale for linking prescriptions and diagnosis made in secondary care. However, information on patient anthropometric data (height, weight, BMI) are not available through the databases, nor are lab results and clinical measurements such as HbA1c, blood pressure and blood lipid levels.

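### The T2DM row of Table 9.3.2-1 is narrower than the Section 9.3 definition: it omits O24.1, already extracted as a pregnancy code, so a pregnant woman with coded type 2 diabetes can be counted as having no T2DM

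*Protocol*

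**What the plan says.** Section 9.3 gives four alternative routes to T2DM. They are a diagnosis ("with any recorded diagnosis code for T2DM"), a non-insulin drug ("or with any recorded treatment code for an ADM other than insulin"), insulin started after age 30, and unspecified diabetes ("or with any record of unspecified diabetes mellitus diagnosis at age >30 and without history of insulin therapy").

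The T2DM row of Table 9.3.2-1 also has four routes: "ICD-10 code E11"; "ATC codes A10P or A10X"; "ATC codes A10A initiated at age>30"; and E14 first recorded after age 30 with no insulin code in the preceding six months.

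The pregnancy row of the same table reads "A34, E23.0, F53, M83, O00-O99, O24.1, O24.3, O24.9, Z32-Z36, Z39". It names O24.1 and O24.3 individually although O00-O99 already covers them. Neither appears in the T2DM row.

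Section 9.3 counts two groups as off-label: patients who do not meet the T2DM definition, and T2DM patients with no other anti-diabetes medication (ADM) in the six-month baseline. The mock table (Table 9.7.4-1) gives each group its own row. The secondary objective reports off-label use within each population of interest, pregnant and breastfeeding women included.

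**The concern.** The text accepts any T2DM diagnosis code, and the table accepts one. The code left out is specific to pregnancy, so the gap falls on one of the populations for which off-label use is a stated objective. A woman whose type 2 diabetes is recorded only under the obstetric code would have that record used to put her in the pregnant column, and ignored when her diabetes is classified.

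At stake is the off-label entry of that column: its total for some women, and only its split into two rows for others.

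**Working it through.** No figure in the plan depends on this point, so the check sets the rules side by side and runs example patients through them.

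**Inputs.** The T2DM routes are those of Section 9.3 and Table 9.3.2-1. The title page gives dulaglutide the ATC code A10BX. Table 9.3.2-1 lists metformin's class, the biguanides, as A10BA. The protocol does not spell out what O24.1 and O24.3 mean. I take the meanings from ICD-10, the classification it adopts: O24.1 is pre-existing type 2 diabetes in pregnancy, and O24.3 is pre-existing diabetes of unspecified type.

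**Classification as T2DM.** All examples are pregnant initiators. Ages are illustrative and refer to the first record of the insulin or diagnosis. The text column does not count dulaglutide as its own qualifying drug.

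| Record besides dulaglutide | Table row | Section 9.3 text | Table row after the fix |
|---|---|---|---|
| O24.1 only, age 28 | no | yes | yes |
| O24.1 and metformin, age 28 | no | yes | yes |
| O24.1 and new insulin, age 28 | no | yes | yes |
| O24.1 and new insulin, age 35 | yes | yes | yes |
| O24.1 and E11, age 28 | yes | yes | yes |
| O24.3 only, age 28 | no | no | no |
| O24.3 only, age 35 | no | yes, if O24.3 counts as unspecified diabetes | yes |

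The first three lines show the gap. The insulin and E14 routes are closed at age 30 or younger. Metformin does not help under the table, because its non-insulin route lists A10P and A10X but not A10B.

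**Effect on off-label status.**
- O24.1 with metformin or insulin in the baseline period: the table makes her off-label without T2DM. With O24.1 accepted she has T2DM and another ADM, so she is not off-label.
- O24.1 with no other baseline ADM: the table makes her off-label without T2DM. With O24.1 accepted she is off-label as first-line use. The off-label total is unchanged and only the row moves.

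**Size.** In a column of n women, each one misclassified moves a percentage by 100/n points: 100/2 = 50, 100/5 = 20, 100/10 = 10. These values of n are assumptions, and the arithmetic holds for any error in a small column. The documents give neither the number of pregnant initiators nor the number with O24.1 but no E11.

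The sensitivity analysis in Section 9.7.3 varies only the age limit on the insulin and E14 routes, so it would not reveal the gap.

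**The case against.** The strongest reply is that Section 9.3 is not wrong. Its diagnosis line already admits O24.1, and the off-label rule points back to that definition, not to the table. Applied as written, the text does not misclassify these women. This stands as far as it goes: the defect is in the table. But Section 9.3.2 says the ICD-10 codes are those presented in the protocol and leaves only the Read codes to the SAP, so the table is what would be programmed.

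A second reply is that the text accepts any non-insulin ADM at any age, which would rescue a woman on metformin. That is also true of the text, but the table omits A10B. Read literally, the text would even count dulaglutide itself, and the planned row for patients without T2DM would be empty. That is a wider conflict between text and table, and it affects every patient.

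Third, Section 9.9.1 concedes that diagnoses may be missing or misreported and says treatment codes will compensate. That covers absent diagnoses, not a recorded diagnosis that is missing from the list.

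A reader might also infer more than the documents support:
- E11 is not the only diagnosis route; E14 after age 30 without recent insulin is another.
- O24.3 is not coded type 2 diabetes. It parallels E14.
- It is tempting to place the problem in Sweden, because the patient register is described as "covering all specialist and hospital care in Sweden" and an E11 recorded only in primary care would not be seen. Nothing in the protocol shows that such women would instead carry O24.1 without E11, and Sweden is only a candidate country.
- A material bias in the off-label results cannot be claimed, since no count is available.

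**Conclusion.** The point holds as a mismatch between text and table. The T2DM row does not implement the Section 9.3 diagnosis route, because it leaves out a type-2-specific code that the same table already extracts.

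A woman is misclassified only if she is recorded as pregnant at initiation, has O24.1, has no E11 anywhere in her record, and meets no other route in the row (A10P or A10X at any age; new insulin, or E14 without insulin, after age 30). Only those with another ADM at baseline are moved wrongly into off-label use; for the rest the sub-row alone is wrong.

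The number affected is unknown and probably very small, given how limited pregnancy recording is said to be in Table 9.4.5-1 and Section 9.9.1. The conclusion rests on the ICD-10 meaning of O24.1 and on the table being the operative code list. It is a minor correction.

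**What to change.** In the T2DM row of Table 9.3.2-1:
- Let O24.1 qualify on the same footing as E11.
- Let O24.3 qualify under the same age and insulin conditions as E14. A woman aged 28 with O24.3 alone then remains without T2DM, as she would with E14 alone.
- Keep gestational diabetes codes out.
- Mirror both additions in the Read code list for CPRD.

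At the same time, reconcile the row with Section 9.3 on the non-insulin drug route: state whether A10B drugs qualify, and whether dulaglutide's own A10BX code counts.

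The cost is two codes in a list and a short clarification. No new data are needed, since both codes are already extracted.

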- Patients having at least 6 months of available continuous history prior to the date of the first dulaglutide prescription.

No exclusion criteria will be applied.

Subgroups of interest:

- Populations of interest:
 - Patients with severe renal failure
 - Patients with hepatic disease
 - Patients with heart failure
 - Patients with severe gastrointestinal disease
 - Children and adolescents <18 years of age
 - Elderly patients ≥ 75 years
 - Pregnant and breastfeeding women
- Medication use:
 - Medication errors
 - Off-label use

Variables:

The following variables will be extracted from databases, whenever available, which will be analysed at the baseline (6-month period prior to dulaglutide initiation) and/or index date (dulaglutide initiation):

- Patients' demographics (age and gender) at baseline
- Relevant comorbidities
- Medical history: disease diagnoses

- Concomitant anti-diabetes medications (ADMs) and other drug exposures
- Average daily dosage of prescriptions
- Prescriptions in combination with other ADMs

Data sources:

The following European EHR databases will be used for the feasibility. A subset of these databases will be then selected for the actual study:

- France: IMS Disease Analyzer (French DA)
- Germany: IMS Disease Analyzer (German DA)
- Spain: The Information System for the Development of Research in Primary Care (SIDIAP)
- Sweden: National Patient Register (NPR) and Swedish Prescribed Drug Register (SPDR)
- United Kingdom: Clinical Practice Research Datalink (CPRD)

Study size:

The first analysis and report will commence once at least 1000 patients initiated with dulaglutide become available in the EHR databases with at least 100 patients in the smallest country. All eligible patients of each selected database will be included in the study. Such a sample size would provide a precision of 3% for the entire sample and a minimum precision of 10% for the country with the smallest sample around an estimated proportion of 50% with 95% confidence intervals.

Data analysis:

The analysis will be performed per country, on the overall data set of eligible patients, 0.75 or 1.5 mg prescription of dulaglutide, and per subgroups.

Data coming from different databases/countries will not be pooled. The analysis will be done per year, and will not be cumulative. Thus data coming from different years will not be pooled either.

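### The T2DM definition has no limit at the index date and, in the prose, counts dulaglutide itself, so the off-label row for patients without T2DM is emptied or understated

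*Protocol*

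**What the plan says.** Section 9.3 of the protocol gives four alternative routes to T2DM status. The first two are "with any recorded diagnosis code for T2DM" and "or with any recorded treatment code for an ADM other than insulin". The other two are insulin started after age 30, and an unspecified diabetes diagnosis after age 30 without earlier insulin. The T2DM row of Table 9.3.2-1 repeats the scheme in codes, for example "ICD-10 codes E14 first recorded at age>30 without ATC code A10A in the previous 6 months". Its non-insulin drug route is limited to ATC A10P or A10X. Neither place sets an end date relative to dulaglutide initiation.

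Off-label use has two limbs. The first is "Prescribed dulaglutide with no diagnosis of T2DM as defined above", so it takes over the undated rule. The second is T2DM under the same rule with no other anti-diabetes drug (ADM) in the 6-month baseline, which is a dated test. Table 9.7.4-1 reports the limbs as separate rows.

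The only general timing statement that might apply is in the abstract, where variables are to be "analysed at the baseline (6-month period prior to dulaglutide initiation) and/or index date (dulaglutide initiation").

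Section 9.1 has the data extracted after each initiation year has closed: "1st wave: Q3 2016 (covering patients having initiated the drug from Q1 to Q4 2015") and "2nd wave: Q2 2017 (covering patients having initiated the drug from Q1 to Q4 2016"). Wave 3 follows the wave 2 pattern one year later.

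**The concern.** Off-label use belongs to both the primary and the secondary objective, and it should describe what was known when dulaglutide was prescribed. The rule as written lets two kinds of record decide that status wrongly.

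- **The index prescription.** Dulaglutide is a non-insulin ADM, so the prose route is met by the prescription that brings the patient into the study.
- **Later records.** Every extract will contain post-index data, and the medication-error measure needs it, because it uses the next prescription. A T2DM code or another ADM first recorded after initiation would class the patient as having had T2DM at initiation.

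Both errors act in one direction on the without-T2DM row: they can only remove patients from it. Patients with no baseline ADM then enter the first-line row, which Section 9.9.1 already calls an overestimate for a different reason. The sensitivity analysis in Section 9.7.3 varies only the age threshold and would not show either effect.

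**Working it through.** **1. Plan's own figure.** The protocol gives no figure for this point. Its only calculations are the study sizes. With n = 0.25 z²/e² and z = 1.96 they come to 384.1, 1067.1 and 96.0, against the stated 384, 1066 and 97. They play no part here.

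**2. Literal reading of the prose.** The PASS information table gives dulaglutide the code A10BX, and it is not insulin. Every initiator therefore meets the drug route on the index date, and the without-T2DM row is 0 whatever is recorded later.

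**3. Reading of the table.** A10P or A10X does not include A10BX, so dulaglutide does not qualify. But the same table lists biguanides, sulfonylureas and most other non-insulin agents under A10B, and these would not qualify either. The prose and the table therefore define different populations.

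**4. Who moves, with dulaglutide excluded and later records allowed.**

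| Patient at index (no qualifying record) | Later T2DM code or other ADM | Effect on total off-label |
|---|---|---|
| No ADM in the 6-month baseline | Without-T2DM row to first-line row | None |
| Non-qualifying baseline ADM, e.g. insulin first recorded at age 30 or younger | Leaves both rows | Falls |

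**5. Post-index record time, before data lag (Section 9.1).**
- Wave 1: 18 to 21 months for a January starter and 6 to 9 for a December starter. With extraction at mid-quarter and even starts, the window is 7.5 to 19.5 months, mean 13.5.
- Waves 2 and 3, identical: 15 to 18 and 3 to 6 months. The window is 4.5 to 16.5 months, mean 10.5.

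Table 9.5.2-1 gives data lags of 1 month (France), 6 weeks (Germany), 6 months (Sweden) and 1 year (Spain); the UK cell is blank.

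**6. Illustration.** Let h be the monthly rate at which a patient without T2DM acquires a first qualifying record. The protocol gives no rate, so 1%, 2% and 5% are assumptions. Over a window from a to b, the mean share recoded is 1 − (e^(−ha) − e^(−hb)) / (h(b − a)). For wave 1 with no lag and h = 0.02: 1 − (0.8607 − 0.6771)/0.24 = 23.5%.

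| Data lag | Wave 1, h = 1% / 2% / 5% | Waves 2 and 3, h = 1% / 2% / 5% |
|---|---|---|
| None | 12.6 / 23.5 / 48.3% | 9.9 / 18.7 / 40.0% |
| 6 weeks (1.4 months) | 11.3 / 21.3 / 44.6% | 8.6 / 16.4 / 35.6% |
| 6 months | 7.2 / 13.7 / 30.2% | 5.1 / 9.8 / 22.2% (captured initiators only) |

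If the true share without T2DM is 10% (assumed), the reported share runs from 10% × (1 − 0.483) = 5.2% to 10% × (1 − 0.051) = 9.5%. With an index-date cut, later records recode nobody.

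**7. What drives the size.** At h = 2%:
- Wave 1 against waves 2 and 3, no lag: 23.5 − 18.7 = 4.8 points.
- No lag against a 6-month lag, wave 1: 23.5 − 13.7 = 9.8 points.
- January against December starter, wave 1, no lag: (1 − e^(−0.39)) − (1 − e^(−0.15)) = 32.3% − 13.9% = 18.4 points.

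Initiation month and database lag matter more than wave.

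**The case against.** **Timing is already covered, or belongs in the SAP.** The abstract refers to baseline and index date, Table 9.3.2-1 dates the subgroup comorbidities to initiation of treatment, and Section 9.7.4 dates medications. But none of these names T2DM status. Renal, hepatic and heart disease are undated in the Section 9.3 prose too, yet the table dates them; T2DM is undated in both places. Read as a 6-month look-back, the abstract would contradict the any-recorded wording and lose T2DM coded earlier. The protocol writes this rule out in full and does not defer it, so the conflict is in the protocol itself.

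**A later code may be correct.** This stands in part. Section 9.9.1 expects missing diagnoses, especially in primary care, and the Swedish diagnoses come from specialist and hospital care only. A T2DM code entered after initiation may be late capture of existing disease, and a strict cut would then overstate the without-T2DM row. This calls for a sensitivity analysis; it does not justify an open-ended rule as the main definition.

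**The wave effect is small.** This stands. A reader might infer that the bias differs in every wave and that the yearly results cannot be compared. Waves 2 and 3 share one schedule, and wave 1 differs by one quarter. On the assumed 10% base, the wave gap in the table above is 0.2 to 0.9 percentage points. The 95% half-width at 10% is 1.96 × √(0.1 × 0.9/1000) = 1.9 points for 1,000 patients and 5.9 points for 100. Starts concentrated late in the launch year would shrink the gap further, and the protocol plans no between-year test.

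**Conclusion.** The definition needs correcting. Under the Section 9.3 prose taken literally, the without-T2DM row is empty. Once dulaglutide is excluded, records made after initiation still bias that row downward. These are alternative readings, and their effects do not add up.

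The size of the second effect is not known from the documents. The range of 5.2% to 9.5% reported for a true 10% rests on an assumed base share, assumed monthly rates, even starts and mid-quarter extraction. It shows that the effect need not be negligible and estimates nothing.

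A reader might also infer that off-label use as a whole disappears. It does not: patients with no baseline ADM change rows and stay in the total. Only those with a baseline ADM that did not itself qualify them, such as insulin first recorded at age 30 or younger, drop out. Nor do the documents support calling the yearly results non-comparable. The study size is unaffected.

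**What to change.** - In Section 9.3, Table 9.3.2-1 and Section 9.7.3, state that T2DM status is set from all available records dated on or before the index date, and that dulaglutide itself is not counted.
- Reconcile the non-insulin drug codes in the T2DM row of Table 9.3.2-1 (A10P or A10X) with the prose, which covers any non-insulin ADM.
- As a sensitivity analysis, report the two off-label rows with post-index T2DM diagnosis codes also accepted, once within a short window (for example 30 days, a suggestion with no source in the protocol) and once at any time. The spread shows how much late coding matters in each database.

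The cost is one sentence in each place, one date filter and a few extra table rows. The downside is small: some late-coded T2DM patients will appear as without T2DM in the main analysis, and the sensitivity analysis makes that visible.
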